6.2 Methods of minimizing bias

(ICH/E6 6.4.3; AGEK 4.3; SPIRIT #16, 17)

ICH: A description of the measures taken to minimize/avoid bias, including: Randomization, Blinding.

In order to minimize bias, the following measures will be taken:

6.2.1 Randomization

As this is a controlled cross-over study each subject serves as his or her own control. For the reduction of order effects the sequence of the tested settings (and/or tested devices) will be randomized. To do so block randomization will be used. The randomization is applied to all investigational settings for both the laboratory trials and the trials in real world environment. For sub-studies with several test methods the order of the test methods will be also randomized with help of block randomization. Randomization and concealment of randomization list is generated by the Principle Investigator. For laboratory tests where several individual ratings are executed with help of computer controlled testing procedures (e.g. software tool for MUSHRA test) simple randomization is applied to the sequence of the respective settings. This simple randomization is done automatically by the tool, the individual simple randomization can be examined afterwards.

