1.3 Statistician ("Bios tatis tician")

(ICH/E6 6.1.7; SPIRIT 5a-d)

ICH: Name(s) and address(es) of the clinical laboratory(ies) and other medical and/or technical department(s) and/or institutions involved in the trial.

The role as the Statistician is adopted by the Principle Investigator.

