6.1 General study design and justification of design

(ICH/E6 6.4.2, 6.4.5; AGEK 4.2; SPIRIT #8)

ICH: The scientific integrity of the trial and the credibility of the data from the trial depend substantially on the trial design.

ICH: A description of the type/design of trial to be conducted (e.g., double-blind, placebo-control led, parallel design) and a schematic diagram of trial design, procedures and stages.

ICH: The expected duration of subject participation, and a description of the sequence and duration of all trial periods, including follow-up, if any.

A methodical evaluation of novel sound changing principles in CE-Labelled Sonova brand hearing instruments (primarily Phonak hearing instruments) is intended to be conducted on hearing impaired and normal hearing subjects. This will be a controlled, single blinded (participants), randomised (sequence of test procedure and sequence of tested setting/device), cross-over (investigational product/setting) active comparator study which will be conducted mono centric at Sonova AG Headquarters based in Stäfa.

Treatments/Interventions:

Hearing systems (hearing instruments with hearing instrument software and respective acoustic coupling, fitting software and wireless accessories). All CE labelled MDs.

Population:

Adult participants with different degrees of hearing abilities. In the pre-studies it is planned to include up to 5 participants. The main studies will normally include 20 - 25 participants each. If possible a power analysis is carried out for each study to determine the necessary number of subjects.

Level and method of blinding/masking:

The tests will be at least single blinded.

When testing different parameter settings of the novel application and/or comparing novel with previous applications whereas these approaches are available as optional settings in one hearing instrument, the subjects will not know which setting is activated during the respective testing.

In cases where these settings are not accessible in one hearing instrument (e.g. previous sound changing principle is not supported by the latest hearing instrument technology any more), the test needs to be undertaken with several (two) separate hearing instruments, whereas the housing of these hearing instruments may differ. The subjects will not be informed about the setting or the sound changing principle in the specific hearing instrument.

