7.2 Recruitment and screening

(Clin O, Art 25, Appendix 3, 1.4 & 1.6; AGEK 5.1; SPIRIT #15)

The recruitment will take place outside the study site for external subjects and will also take place internal (at Sonova) for internal subjects.

At Sonova AG Headquarters, a participant database is existing which is currently containing approx. 700 hearing impaired subjects (various degrees of hearing loss) from circumjacent cantons. Furthermore, this database is containing hearing impaired employees from Sonova AG (internal subjects). The database is permanently extended (study independently) with new subjects recruited via different paths and screened by qualified Audiologists employed at Sonova AG. One examples for this recruiting is a flyer for Phonak Field studies (see attachment: Flyer_Phonak_Feldstudie.pdf).

Recruitment and screening outside:

The pre-selection of suitable participants will be done by the principal investigator after receiving the study approval of the responsible CEC by using the participant database belonging to the study site.

The preselected participants will be listed in a password locked file. Only the study personal will have access to this file. The preselected potential participant will be contacted via telephone. At this initial contact, the time expenditure and the availability period will be discussed. If a participant is interested in participating in the study, the screening appointment for a preliminary clarification will be arranged and the participant information and informed consent will be sent to the potential participant by post or email at least one week before the screening appointment takes place. The assessment of the screening serves to judge the inclusion criteria (e. g. pure tone audiometry), giving answers to any questions which the subjects may have, giving information about the study and sign of the informed consent.

For all study related appointments at Sonova AG, the participants will receive a compensation of 25 CHF/hour and a SBB train ticket (2nd class) from their home address to Sonova AG, [name], by the end of the study.

Recruitment and screening inside:

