The participants are recruited by the study team in the according study site (Sonova AG). The participants are employees at the study site. The pre-selection of suitable hearing impaired participants will be done by the principal investigator after receiving the study approval of the responsible CEC by using the participant database belonging to the study site.

The time expenditure and the availability period will be directly discussed with the participant. If a participant is interested in participating in the study, the screening appointment for a preliminary clarification will be arranged and the participant information and informed consent will be sent to the potential participant by email at least one week before the screening appointment takes place. The assessment of the screening serves to judge the inclusion criteria (e. g. pure tone audiometry), giving answers to any questions which the subjects may have, giving information about the study and sign of the informed consent.

The participants participate on a voluntary basis and contribute to an investigational benefit for the company.

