11.4.1 Datasets to be analysed, analysis populations

ICH: The selection of subjects to be included in the analyses (e.g., all randomized subjects, all dosed subjects, all eligible subjects, evaluable subjects).

The data of all participants and measurement methods will be analysed. Subgroups typically composed are hearing loss dependent groups (mild, moderate, severe, profound) and groups depending on their experience level wearing hearing instruments or using accessories (non-experienced, short-term, experienced, long-term user). In case of a subject withdrawal, the statistician will decide if the data can be used for a part of the statistical analysis or if the data will be dropped out completely.

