11.4.2 Primary Analysis

The primary analysis will be done by the statistician with help of appropriate software programs (e.g. Matlab, Statistica) by the end of the study (end of the pre-study and end of the main study).

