11.5 Handling of missing data and drop-outs

(ICH/E6 6.9.5; AGEK 8.5; SPIRIT 20c)

ICH: Procedure for accounting for missing, unused, and spurious data.

If data records are complete from subjects who dropped out of the study early, these data will also be used in the analysis. If the data sets are not complete, they will not be integrated in the analysis.

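### The Principal Investigator pre-selects participants, makes the order list and, as statistician, has open discretion over withdrawn data that conflicts with the plan's own completeness rule; no masked analysis is described

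*Combined protocol and SAP*

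**What the plan says.** **Roles.**

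- Order list (6.2.1): "Randomization and concealment of randomization list is generated by the Principle Investigator".
- Statistician (1.3): "The role as the Statistician is adopted by the Principle Investigator".
- Recruitment (7.2): for external participants, "The pre-selection of suitable participants will be done by the principal investigator"; for employees, "The pre-selection of suitable hearing impaired participants will be done by the principal investigator".
- Analysis (11.4.2): "The primary analysis will be done by the statistician with help of appropriate software programs". Section 11.4.3 handles the secondary analysis in the same way.

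**Withdrawn data.** Section 11.4.1 says that after a withdrawal "the statistician will decide if the data can be used for a part of the statistical analysis", or is dropped altogether. Section 11.5 leaves no such choice: "If the data sets are not complete, they will not be integrated in the analysis". Sections 7.4 and 8.5 also tie inclusion to completeness.

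**Test.** Section 11.4 lists parametric and non-parametric tests and selects among them by scale level and by the distribution found in the data, at a 5% level. Section 11.1 states that no specific hypothesis is tested.

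**Blinding.** Section 6.1: "The tests will be at least single blinded". The blinded party is the participant. Double blinding is conditional and relies on computer-controlled test procedures (6.1, 6.2.2). Section 6.2.3 adds that investigators are made aware of bias. No section describes a separate list holder, coded settings in the data, or an analyst who is unaware of the setting.

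**The concern.** A list cannot be concealed from the person who writes it, and here that person also chooses who is approached. In a parallel-group trial this would be a serious route to selection bias. In this cross-over it is a smaller matter, since it can affect only which participant gets which order.

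The larger matter comes later. The same person analyses the data, may decide case by case whether a withdrawn participant counts, and picks the test once the data are visible. With 20 to 25 participants per main study (11.2), a few records can move a p-value across 5%. Sections 5.1 and 9.2.1 intend to conclude whether the experimental condition is superior to its comparator. The error rate of that conclusion is protected only if the data set and the test do not depend on the result. Because 11.4.1 disagrees with 7.4, 8.5 and 11.5, the plan does not even settle which rule applies.

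**Working it through.** **1. Rules for withdrawn data, side by side.**

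| Section | Rule |
|---|---|
| 7.4 | Excluded if not complete enough for the analysis |
| 8.5 | Included if complete for the trial concerned |
| 11.5 | Complete records used; incomplete data sets not used |
| 11.4.1 | Statistician decides: partial use, or dropped completely |

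The first three do not depend on results, although 8.5 judges completeness by trial and 11.5 by data set. The fourth states no criterion. They cannot all govern.

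**2. Size of the risk.** The documents give no drop-out rate, effect size or standard deviation, and the plan offers no figure to reproduce here. Inputs:

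- 20 completers, the lower end of the range in 11.2;
- 1, 2 or 3 withdrawn participants with a usable contrast (assumed);
- normal within-participant differences with no true effect (assumed);
- 5% level from 11.4, taken as two-sided because the sidedness is not stated. That leaves 5% / 2 = 2.5% for a false finding in favour of the novel setting.

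The worst case is an analyst who computes p for every subset of the withdrawn participants, by t-test and by Wilcoxon, and reports the smallest. With k withdrawn there are 2^k × 2 candidate p-values: 4, 8 and 16 for k = 1, 2 and 3.

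| Withdrawn | Rule and test fixed | Labels known | Labels coded |
|---|---|---|---|
| 1 | 2.5% | about 3.5% | about 3.5% |
| 2 | 2.5% | about 4.0% | about 4.0% |
| 3 | 2.5% | about 4.8% | about 4.8% |

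The excess is 1.0, 1.5 and 2.3 percentage points. Separate runs of 4,000 to 20,000 simulated trials gave 2.8% to 3.6%, 4.0% to 4.3% and 4.7% to 5.1%. At 4,000 trials the standard error near 4% is √(0.04 × 0.96 / 4000) = 0.3 points, so this spread is mostly simulation noise. Free choice of test with no withdrawals gave only about 2.8%.

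**3. Sensitivity.** Here the error is two-sided, only the t-test is used, and the withdrawn are counted within the total. With nothing left to choose, the simulated error was 4.9% to 5.3%.

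| Withdrawn | N = 20, all or none | N = 20, one by one | N = 25, all or none | N = 25, one by one |
|---|---|---|---|---|
| 1 | 6.3% | 6.3% | 6.0% | 6.0% |
| 2 | 6.4% | 7.3% | 6.3% | 7.1% |
| 3 | 7.0% | 8.9% | 6.7% | 8.4% |

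**4. Why coding alone does not help.** An analyst who sees only A and B can search for the smallest two-sided p and find the same extremes; half of them favour the novel setting. This is why the two label columns agree. The inflation comes from choosing after seeing results.

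**The case against.** **The design limits the damage.** Every participant receives every setting, so foreknowledge of the list affects only order. What remains is a period, learning or carry-over effect that differs between participants. This stands, and the point does not rest on selection bias.

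**Three sections already give a results-free rule.** Section 11.4.1 might be read as merely applying it: data complete for one part are used for that part. That reading fits 8.5, but 11.4.1 names a decision by the statistician and no criterion. The conflict needs repair even if nobody ever uses the latitude.

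**The simulated behaviour is a worst case.** Section 11.4 ties the test to the distribution and not to the smaller p-value. This also stands: the figures are upper illustrations and not a prediction.

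**Stronger readings that the documents do not support.** A reader might infer any of the following.

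- That there is no concealment at all. Participants are to be kept unaware (6.2.2), concealment from other investigators is not ruled out, and in computer-controlled rating tests the tool generates the order (6.2.1).
- That the Principal Investigator conducts the laboratory tests. No section says so, and the synopsis mentions further investigators on a staff list.
- That unblinding causes the inflation. The calculation shows otherwise. That the analyst knows the settings is itself inferred from the absence of any stated masking.

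**Conclusion.** The point holds in limited form. The concentration of roles is documented, the order list cannot be concealed from its author, and no masked analysis is described. The discretion in 11.4.1 contradicts the completeness rule in 7.4, 8.5 and 11.5.

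The consequence is moderate. With 20 completers and 1 to 3 usable withdrawals, a fully results-driven choice of data and test could raise false superiority from 2.5% to about 3.5% to 5%, which is at most about a doubling. This rests on an assumed number of withdrawals, normal differences, a two-sided 5% level and worst-case behaviour. It says nothing about what the sponsor will in fact do. The change is worth making because it is cheap and the same procedure is repeated across sub-studies over 10 years.

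**What to change.** - **11.4.1:** replace the statistician's discretion with the single completeness rule of 11.5. Reconcile 7.4 and 8.5 with it, including whether completeness is judged by trial or by data set.
- **11.4 and 11.4.2:** name the primary test for each sub-study. Record the exclusions and the test in a signed and dated note before any comparison between settings is computed. Signing only before the codes are opened is too late, because coded results permit the same search.
- **Data:** store settings under neutral codes (A, B, C) until that note is signed.
- **6.2.1:** have the block-randomised list generated by software and held by an existing team member who does not recruit or analyse in that sub-study. The staff list in the synopsis suggests that this is feasible, but the documents do not show who is free of those tasks.

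The cost is minor coding work and one signed note per sub-study. No additional participants, visits or devices are needed.

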6.2.2 Blinding procedures

Trial participants will be blinded after assignment to interventions. The subjects will not know which hearing instrument technology they are wearing or which hearing instrument setting is activated during the respective testing (Please refer to section 6.1 General study design and justification of design). If possible double blinding will be executed with help of computer controlled testing procedures (e.g. software tool for MUSHRA Test).

6.2.3 Other methods of minimizing bias

In addition the following methods will be carried out:

- Sensitizing the investigators to bias (e.g. Halo-Effects).
- Application of standardized test methods according to their instructions to avoid training effects
- Usage of validated questionnaires to the greatest possible extent. However, specifically adapted questionnaires are inevitable to validly capture the appropriate information needed
- Orthogonal design of the questionnaires to fulfil the criteria for test quality (objectivity, validity, reliability)
- Limited information will be given to the subjects regarding the products and the sound changing principles being tested
- In order to ensure a high satisfaction of the subject, the physical position in and on the ear must be comfortable and it must be ensured that the subject can operate the device well (e. g. putting the hearing instruments on, changing batteries, switching on/off). These aspects will be observed and checked throughout the study sections so that they are not the form factor to cause any bias in results, especially subjective results

6.3 Unblinding Procedures (Code break)

(ICH/E6 6.4.8; AGEK 4.2; SPIRIT #17b)

ICH: Maintenance of trial treatment randomization codes and procedures for breaking codes.

N/A

7. STUDY POPULATION

(ICH/E6 6.2.6, 6.4.6; AGEK 3.2, 5; SPIRIT #9, 10, 15, 16, 21)

ICH: Description of the population to be studied.

This section describes the population to be studied.

7.1 Eligibility criteria

(Clin O, Art 25d5; ICH/E6 6.5.1&6.5.2; AGEK 5.2&5.3; SPIRIT #10)

ICH: Subject inclusion and exclusion criteria.

Only adult subjects will participate. Hearing impaired subjects as well as normal hearing subjects will participate, the latter as a control group.

Participants fulfilling all of the following inclusion criteria are eligible for the study:

- Adult (minimum age: 18 years) hearing impaired subjects both with and without (experience with) hearing aids
- Adult normal hearing subjects (minimum age: 18 years)
- Healthy outer ear (without previous surgical procedures)
- Ability to fill in a questionnaire conscientiously
- Informed Consent as documented by signature

The presence of any one of the following exclusion criteria will lead to exclusion of the participant:

- Contraindications to the MD in this study, e.g. known hypersensitivity or allergy to the investigational product
- Limited mobility and not in the position to attend weekly appointments
- Limited ability to describe listening impressions/experiences and the use of the hearing aid
- Inability to produce a reliable hearing test result
- Massively limited dexterity
- Known psychological problems
- Known central hearing disorders

7.2 Recruitment and screening

(Clin O, Art 25, Appendix 3, 1.4 & 1.6; AGEK 5.1; SPIRIT #15)

The recruitment will take place outside the study site for external subjects and will also take place internal (at Sonova) for internal subjects.

At Sonova AG Headquarters, a participant database is existing which is currently containing approx. 700 hearing impaired subjects (various degrees of hearing loss) from circumjacent cantons. Furthermore, this database is containing hearing impaired employees from Sonova AG (internal subjects). The database is permanently extended (study independently) with new subjects recruited via different paths and screened by qualified Audiologists employed at Sonova AG. One examples for this recruiting is a flyer for Phonak Field studies (see attachment: Flyer_Phonak_Feldstudie.pdf).

Recruitment and screening outside:

The pre-selection of suitable participants will be done by the principal investigator after receiving the study approval of the responsible CEC by using the participant database belonging to the study site.

The preselected participants will be listed in a password locked file. Only the study personal will have access to this file. The preselected potential participant will be contacted via telephone. At this initial contact, the time expenditure and the availability period will be discussed. If a participant is interested in participating in the study, the screening appointment for a preliminary clarification will be arranged and the participant information and informed consent will be sent to the potential participant by post or email at least one week before the screening appointment takes place. The assessment of the screening serves to judge the inclusion criteria (e. g. pure tone audiometry), giving answers to any questions which the subjects may have, giving information about the study and sign of the informed consent.

For all study related appointments at Sonova AG, the participants will receive a compensation of 25 CHF/hour and a SBB train ticket (2nd class) from their home address to Sonova AG, [name], by the end of the study.

Recruitment and screening inside:

The participants are recruited by the study team in the according study site (Sonova AG). The participants are employees at the study site. The pre-selection of suitable hearing impaired participants will be done by the principal investigator after receiving the study approval of the responsible CEC by using the participant database belonging to the study site.

The time expenditure and the availability period will be directly discussed with the participant. If a participant is interested in participating in the study, the screening appointment for a preliminary clarification will be arranged and the participant information and informed consent will be sent to the potential participant by email at least one week before the screening appointment takes place. The assessment of the screening serves to judge the inclusion criteria (e. g. pure tone audiometry), giving answers to any questions which the subjects may have, giving information about the study and sign of the informed consent.

The participants participate on a voluntary basis and contribute to an investigational benefit for the company.

7.3 Assignment to study groups

(AGEK 5; SPIRIT #16)

This study will be a controlled cross-overs study with active comparator whereas each subjects will receive the intervention to be tested (hearing systems with novel sound changing principles) as well as the respective comparator and serves therefore as his or her own control. For the reduction of order effects the sequence of the test procedures as well as the sequence of the tested settings (and/or tested devices) will be randomized. The randomization is applied to all investigational settings for both the laboratory trials and the trials in real world environment . (refer to 6.2.1 Randomisation).

